11. PROPERTY AND COMMUNICATION OF RESULTS

Pfizer shall remain the owner of all forms of case reports, data analyses and reports resulting from this study.

Any information obtained from this study shall be considered as confidential, until the analysis and final review, by Pfizer and the members of the scientific committee, have been completed.

11.1. Communication and publication by Pfizer

Pfizer will honour its commitment to publicly disclose the results of the clinical study by publishing them on www.clinicaltrials.gov, www.pfizer.com and/or the European clinical trials database (EudraCT), and other public registers, in accordance with applicable local laws/regulations

11.2. Publication by participating physicians

Pfizer does not object to the members of the scientific committee or participating physicians publishing the results of the study. To prevent the accidental disclosure of confidential information or industrial property, however, these results can only be published following revision and consent by Pfizer. Prior to publication or presentation, a copy of the final text must be sent by the members of the scientific committee or participating physicians to Pfizer for comments. Such comments will be intended to check the scientific content of the proposed publications and/or presentations and to ensure that the data and materials relating to Pfizer's products and activities are fairly, accurately and reasonably presented.

The participating physicians will provide Pfizer with the articles, abstracts, or full text of any planned communications (posters, conference speeches, etc.) at least 30 days prior to submission for publication. If an action is required to protect intellectual property rights, the members of the scientific committee or the participating physician will accept to delay disclosure for a period not exceeding 60 additional days.

The participating physician may request the deletion of any previously undisclosed confidential information (other than the study results) before new publication.

If the study is multi-centric, the participating physician agrees that the first publication will be a joint publication covering all centres. If the document has not been submitted to all participating centres for publication 12 months after the end of the study however, the participating physician is free to publish independently, subject to the other provisions stipulated in this paragraph.

All study-related publications must conform to ethics rules concerning copyright and publication. The publication of results shall also give rise to an article in the financial agreement between Pfizer and the participating physician and/or establishment. In this section, publication by participating physicians, the meaning of the defined terms is that specified in the agreement.

12.2. Role of the Scientific Committee

The purpose of this committee is to validate the study protocol, the case report form (CRF and questionnaires), the results and analysis reports, along with all valuations (communications, publications).

It shall also take part in implementing the therapy management platform and will validate the call scenario, physician compensation and team training.

14.3. Appendix 3: ECOG**ECOG Performance Status**

These scales and criteria are used by doctors and researchers to assess how a patient's disease is progressing, assess how the disease affects the daily living abilities of the patient, and determine appropriate treatment and prognosis. They are included here for health care professionals to access.

ECOG PERFORMANCE STATUS*	
Grade	ECOG
0	Fully active, able to carry on all pre-disease performance without restriction
1	Restricted in physically strenuous activity but ambulatory and able to carry out work of a light or sedentary nature, e.g., light house work, office work
2	Ambulatory and capable of all selfcare but unable to carry out any work activities. Up and about more than 50% of waking hours
3	Capable of only limited selfcare, confined to bed or chair more than 50% of waking hours
4	Completely disabled. Cannot carry on any selfcare. Totally confined to bed or chair
5	Dead

* As published in Am. J. Clin. Oncol.:

The ECOG Performance Status is in the public domain therefore available for public use. To duplicate the scale, please cite the reference above and credit the Eastern Cooperative Oncology Group, Robert Comis M.D., Group Chair.

14.4. Appendix 4: SPC

14.5. Appendix 5: Non-Inclusion Register

Non-inclusion register

PURPOSE OF THE NON-INCLUSION REGISTER

The non-inclusion register serves to compare patients to be included in the RENACALL study with eligible patients who have not been included.

This comparison is used to evaluate inclusion biases and thus to measure their impact on the representativeness of the studied population.

Consequently, the statistical results will be fully usable and publishable.

INSTRUCTIONS FOR FILLING IN THE NON-INCLUSION REGISTER

The non-inclusion register should be filled in during the RENACALL study inclusion period, for all adult patients meeting the inclusion and non-inclusion criteria, but who did not wish to take part in the study.

We remain available to answer any questions on:

PPD

CHARACTERISTICS OF PATIENTS NOT INCLUDED IN THE STUDY

CENTRE NO. |_____|_____|_____|

	Year of birth  month year	Gender  Man  Woman	ECOG performance status  0  1  2  3  4	Reason for non-inclusion  Patient refusal  Other, specify: _____
1.	 month year	 Man  Woman	 0  1  2  3  4	 Patient refusal  Other, specify: _____
2.	 month year	 Man  Woman	 0  1  2  3  4	 Patient refusal  Other, specify: _____
3.	 month year	 Man  Woman	 0  1  2  3  4	 Patient refusal  Other, specify: _____
4.	 month year	 Man  Woman	 0  1  2  3  4	 Patient refusal  Other, specify: _____
5.	 month year	 Man  Woman	 0  1  2	 Patient refusal  Other, specify: _____

	Year of birth	Gender	ECOG performance status	Reason for non-inclusion
			 3  4	
6.	□□/□□□□ month year	 Man  Woman	 0  1  2  3  4	 Patient refusal  Other, specify: _____
7.	□□/□□□□ month year	 Man  Woman	 0  1  2  3  4	 Patient refusal  Other, specify: _____
8.	□□/□□□□ month year	 Man  Woman	 0  1  2  3  4	 Patient refusal  Other, specify: _____
9.	□□/□□□□ month year	 Man  Woman	 0  1  2  3  4	 Patient refusal  Other, specify: _____
10.	□□/□□□□ month year	 Man  Woman	 0  1  2  3  4	 Patient refusal  Other, specify: _____

11.	□□/□□□ month year	 Man  Woman	 0  1  2  3  4	 Patient refusal  Other, specify: _____
12.	□□/□□□ month year	 Man  Woman	 0  1  2  3  4	 Patient refusal  Other, specify: _____
13.	□□/□□□ month year	 Man  Woman	 0  1  2  3  4	 Patient refusal  Other, specify: _____
14.	□□/□□□ month year	 Man  Woman	 0  1  2  3  4	 Patient refusal  Other, specify: _____
15.	□□/□□□ month year	 Man  Woman	 0  1  2  3  4	 Patient refusal  Other, specify: _____

Please enter the date and electronically sign

the non-inclusion register:

A618

A6181213 INTERMEDIATE CARE STUDY PROTOCOL

Amendment no. 3.1, 21 July 2017

Date: |__|__|__|__|__|**2**|__|**0**|__|__|

14.6. Appendix 6: Case report form

A6181213

RENACALL STUDY

Pragmatic evaluation of the impact of a therapy management platform on the management of patients suffering from advanced/metastatic renal cell carcinoma and receiving first line treatment with sunitinib, versus standard follow-up

CASE REPORT FORM

Centre identifier

[figure not shown]
Patient identifier

1 PATIENT INCLUSION AND FOLLOW-UP SCHEMA

Verification of inclusion criteria by the investigator

Patient information/consent by patient's initials and signature on the consent form

Connection to the e-CRF module and e-CRF data input

Therapy management platform call scheme

2 INCLUSION VISIT

Inclusion visit date: ____ / ____ / 20____ (DD/MM/YYYY)

Date of consent signing: ____ / ____ / 20____ (DD/MM/YYYY)

DEMOGRAPHIC CHARACTERISTICS

Month and year of birth	____ / ____ / ____ (mm/yyyy)
Gender	 Male 2  Female

2.1 Verification of eligibility criteria

INCLUSION CRITERIA		
Patient suffering from advanced/metastatic renal cell carcinoma, receiving sunitinib first-line treatment, as per SPC recommendations	 Yes	 No
Resolution (grade \leq 1 according to CTCAE version 4.03 of June 2010) of all acute toxic effects due to radiotherapy or surgical procedure prior to initiation of sunitinib;	 Yes	 No
Man or woman aged 18 or over	 Yes	 No
Patient who can be monitored for 6 months	 Yes	 No
Female patient of child-bearing age using a form of contraception during treatment with Sunitinib and for at least 28 days after termination of treatment with Sunitinib;	 Yes	 No
Patient having signed his/her consent form;	 Yes	 No
Patient affiliated with a social security scheme.	 Yes	 No

A single "no" to one of the criteria negates the patient's eligibility for the study

NON-INCLUSION CRITERIA		
Patient participating in a clinical trial during sunitinib treatment	 Yes	 No
Patient managed by a home hospitalisation service during sunitinib treatment	 Yes	 No
Patient taking part in therapeutic education programmes, or benefiting from nursing consultation, or from any other significant treatment support and likely to impact adverse event management.	 Yes	 No
Patient untreated and/or symptomatic brain metastases prior to sunitinib initiation	 Yes	 No
Patient refusing the use of his/her personal data	 Yes	 No
Patient with an ECOG performance status upon inclusion > 2 ;	 Yes	 No
Serum creatinine > 1.5 times the upper normal limit	 Yes	 No
Patient presenting with a bilirubin level > 2 mg/dl, aspartate transaminase (ASAT) or alanine transaminase (ALAT) ≥ 2.5 times the upper limit of the normal value, or ≥ 5 times the upper limit of the normal value in the presence of liver metastases upon initiation of sunitinib treatment;	 Yes	 No
Patients who are staff members of a centre involved in the study, or close to one of the	 Yes	 No

staff members of a centre directly involved in conducting the study, or patients employed by Pfizer and involved in conducting the study

A single "yes" to one of the criteria negates the patient's eligibility for the study

2.2 Contact form

Please fill in the contact form below and return it to the logistics centre.

M. Mrs

Name: _____

First name: _____

Phone no. 1: _____ Phone no. 2 (optional): _____

Preferred call times: 9am-12pm 12-2pm 2-5pm 5-7pm

Display: Print pre-completed contact form button

2.3 Patient characteristics upon initiation of sunitinib treatment

Month and year of birth (mm/yyyy) _____ / _____

Gender Male 2
 Female

Weight : _____ kg Height: _____ cm BMI: _____ (auto)

ECOG: Yes No

If yes, Date: _____ / _____ / _____ (DD/MM/YYYY)

If yes, score: 0 1 2 3 4

e-CRF instruction: a link shall be added allowing the physician to view the score variables

Karnofsky score: Yes No

If yes, Date: _____ / _____ / _____ (DD/MM/YYYY)

If yes, score: 100% 90% - 80% 70% - 60% 50% - 40% 30% - 10% 0%

e-CRF instruction: a link shall be added allowing the physician to view the score variables

Risk score - Criteria of Heng *et al.*:

Good Poor

Intermediate Not available

Number of risk factors: 0 = Good; 1 to 2 = Intermediate; 3 to 6 = Poor.

e-CRF instruction: a link shall be added allowing the physician to view the risk score variables

2.4 History of the disease

Description of the primitive kidney cancer

Date of initial diagnosis / / (DD/MM/YYYY or MM/YYYY)

(anatomopathology report)

Histology

- Clear cell carcinoma
- Tubulopapillary carcinoma, specify:
 - Type I
 - Type II
- Chromophobe cell carcinoma
- Other, specify: _____

Mixed tumour? Yes No

➔ If Yes, specify the dominant tumour: _____

Stage of the disease - TNM classification

- T0 T1 T2 T3 T4 Tx
- N0 N1 N2 Nx
- M0 M1 Mx

Furhman grade

- I II III IV

Description of the primitive kidney cancer treatment

Nephrectomy: Yes No

Radiotherapy: Yes No

Other: Yes No

If yes, specify: _____

Description of the metastatic renal cell carcinoma

Is the renal cell carcinoma metastatic? Yes No

If yes, Date of appearance first metastases: / / (DD/MM/YYYY or MM/YYYY)

Number of different metastatic sites currently affected:

Give the locations of the metastases:

- | | | | |
|----------------------------|------------------------------|-----------------------------|--------------------------------|
| Lung |  Yes |  No |  Blank |
| Bone |  Yes |  No |  Blank |
| Mediastinum |  Yes |  No |  Blank |
| Liver |  Yes |  No |  Blank |
| Retroperitoneal lymph node |  Yes |  No |  Blank |
| Subclavian lymph node |  Yes |  No |  Blank |
| Adrenal gland |  Yes |  No |  Blank |
| Nephrectomy compartment |  Yes |  No |  Blank |
| Kidney |  Yes |  No |  Blank |
| Brain |  Yes |  No |  Blank |
| Skin |  Yes |  No |  Blank |
| Peritoneum |  Yes |  No |  Blank |
| Gastrointestinal |  Yes |  No |  Blank |

Pancreatic	 Yes	 No	 Blank
Skin	 Yes	 No	 Blank
Other 1	 Yes	 No	 Blank
Other 2	 Yes	 No	≤ Not specified

If yes, please specify: _____

2.5 Medical history and co-morbidities at the time of the inclusion visit

Former or current co-morbidities? Yes No

Diabetes Yes No ➔ if yes, specify current: Yes No
➔ Current treatment: Yes No

Thyroid Yes No ➔ If yes, specify Hypothyroidism
Hyperthyroidism
➔ Specify current: Yes No
➔ Current treatment: Yes No

CerebroVascular Accident (stroke) Yes No ➔ if yes, year: _____ (YYYY)
➔ Current treatment: Yes No

Hypertension Yes No ➔ if yes, specify current: Yes No
➔ Current treatment: Yes No
If yes, year initiated: _____ (YYYY)

Myocardial infarction Yes No ➔ if yes, year: _____ (YYYY)
➔ Current treatment: Yes No

Deep vein thrombosis Yes No ➔ if yes, specify current: Yes No
➔ Current treatment: Yes No

Angina pectoris Yes No ➔ if yes, specify current: Yes No
➔ Current treatment: Yes No

Kidney failure Yes No ➔ if yes, specify current: Yes No
➔ Current treatment: Yes No

Liver failure Yes No ➔ if yes, specify current: Yes No
➔ Current treatment: Yes No

Other Yes No ➔ if yes, specify _____
➔ specify current: Yes No
➔ Current treatment: Yes No

2.6 Haematological and biochemical profile prior to sunitinib initiation

Please fill in the following table:

Date of biological examination: ___ / ___ / 20___ (DD/MM/YYYY)

Haematological profile

Parameters	Value obtained	Value	Unit
Haemoglobin	 Yes  No  Not performed	 g/dL	 Other If other, specify: ___
Neutrophils	 Yes  No  Not performed	 /mm ³	 Other If other, specify: ___
Platelets	 Yes  No  Not performed	 10 ⁹ /L	 Other If other, specify: ___

Biochemical profile

Parameters	Value obtained	Value	Unit
Creatinine	 Yes  No  Not performed	 mg/dL	 Other If other, specify: ___
ALAT (GPT)	 Yes  No  Not performed	 U/L	 Other If other, specify: ___
ASAT (GOT)	 Yes  No  Not performed	 U/L	 Other If other, specify: ___
Total bilirubin	 Yes  No  Not performed	 mg/dL	 Other If other, specify: ___
Calcium	 Yes  No  Not performed	 mmol/L	 Other If other, specify: ___
Albumin	 Yes  No  Not performed	 g/L	 Other If other, specify: ___
LDH	 Yes  No  Not performed	 UI/L	 Other If other, specify: ___

Were abnormal values of other biological parameters observed (last available examination)? Yes No

Parameters	Value obtained	Abnormal result	For abnormal results, value	Unit
Haematology				
Haematocrit	 Yes  No  Not performed	 Yes  No		 %  Other If other, specify: ___
White blood cells	 Yes  No  Not performed	 Yes  No		 10 ⁹ /L  Other If other, specify: ___
Biochemistry				
Alkaline phosphatase	 Yes  No  Not performed	 Yes  No		 U/L  Other If other, specify: ___
TSH	 Yes  No  Not performed	 Yes  No		 mU/L  Other If other, specify: ___
fT3	 Yes  No  Not performed	 Yes  No		 pmol/L  Other If other, specify: ___

fT4	 Yes  No  Not performed	 Yes  No		 pmol/L  Other If other, specify: ____
Sodium	 Yes  No  Not performed	 Yes  No		 mmol/L  Other If other, specify: ____
Potassium	 Yes  No  Not performed	 Yes  No		 mmol/L  Other If other, specify: ____

2.7 Other examinations

Arterial blood pressure

Examination: Yes No

If yes, examination date: ____ / ____ / ____ (DD/MM/YYYY)

If yes, specify values: ____ / ____ mmHg

syst. diast.

Electrocardiogram (ECG)

Electrocardiogram: Yes No

➔ If yes, Date : ____ / ____ / ____ (DD/MM/YYYY)

Normal result: Yes No ➔ if abnormal, specify:

- Atrial fibrillation (AF)
- Ventricular arrhythmia
- Atrioventricular block (AV block)
- Other, specify: _____

Echocardiography

Echocardiography: Yes No

➔ If yes, Date: ____ / ____ / ____ (DD/MM/YYYY)

Normal result: Yes No ➔ if abnormal, specify: _____

Oral examination

Yes No

Oral examination: Yes No

➔ If yes, Date : ____ / ____ / ____ (DD/MM/YYYY)

➔ If yes, Result: Normal Abnormal

2.8 Initiation of Sunitinib first line treatment

Initiation of sunitinib treatment

Date of first day of cycle 1: ____ / ____ / ____ (DD/MM/YYYY)

Dose and dosage regimen:

- 50 mg/day, 4 weeks followed by a 2-week break

2.9 Symptomatic or preventive treatments

Symptomatic or preventive treatments prescribed during the initial visit

- | | | |
|--|------------------------------|-----------------------------|
| Prescription of an anti-emetic treatment: |  Yes |  No |
| Prescription of an anti-diarrhoeal treatment: |  Yes |  No |
| Initiation of anti-neutropenic treatment |  Yes |  No |
| Prescription of an anti-hypertensive treatment: |  Yes |  No |
| Prescription of mouth washes and local anaesthetics: |  Yes |  No |
| Prescription of emollients, moisturising creams: |  Yes |  No |
| Prescription of analgesics: |  Yes |  No |
| Prescription of an anti-gastro-oesophageal reflux treatment: |  Yes |  No |
| Bisphosphonate treatment: |  Yes |  No |
| Other anti-tumour treatment: |  Yes |  No |

If yes, specify: _____

- Other prescriptions: Yes No

If yes, specify: _____

e-CRF instruction: 'Please send an anonymised copy of available prescriptions issued to the patient after the inclusion visit to the logistics centre, to enable the therapy management platform nurses to advise the patient. Each prescription must comprise the patient's participation no.'

2.10 Sunitinib treatment accompanying measures

The information received by the patient upon sunitinib treatment initiation (several boxes possible) was provided:

- by yourself
 by the care team. Specify the type of individuals involved (nurse, intern, etc.)

by means of an information leaflet or any other medium / material / document issued to the patient:

Specify the medium: _____

other: _____

3 FOLLOW-UP VISIT - ROUTINE END-OF-CYCLE CONSULTATIONS

Identical follow-up data collection by the physician for all three visits: W6, W12 and W24.

Follow-up visit date: / / / (DD/MM/YYYY)

Scheduled cycle end date: / / / (DD/MM/YYYY)

3.1 Tumour evaluation

Has a tumour evaluation been carried out since the last visit dated [date of last recorded visit]: Yes No

If yes, examination date: / / / (DD/MM/YYYY)

X-ray examination (several choices possible) performed to determine tumour progression:

Scan MRI PET scan X-ray Echography

Response to treatment according to participating physician, according to RECIST v1.1 criteria

- CR (complete response)
- PR (partial response)
- SD (stable disease)
- PD (progressive disease)
- NA (not assessable)

Reason: _____

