3.5 Conditions of use of the sunitinib treatment

Has the sunitinib dose and/or dosage regimen been changed since the last documented visit dated [date of last recorded visit], including during the day's follow-up visit?

Yes No

If yes, describe all modifications observed:

Date	Change of dose	If yes, new dose (mg/day)	Change of dosage regimen	If yes, new regimen	Reason for the modification
__/__/__ (DD/MM/YYYY)	 Yes  No	 25  37.5  50  62.5  75  Other: __	 Yes  No	: _____	 AE; If yes, specify which one: _____  Other, specify: _____
__/__/__ (DD/MM/YYYY)	 Yes  No	 25  37.5  50  62.5  75  Other: __	 Yes  No	: _____	 AE; If yes, specify which one: _____  Other, specify: _____

(Dynamic table: rows can be added if more than two modifications are observed)

*: If AE ticked, the physician has already described this AE in the previous section, the e-CRF will thus display the list of AEs already filled in and the physician can simply select the relevant AE (without having to describe it again)

Has the sunitinib treatment been temporarily interrupted since the last documented visit dated [date of last recorded visit], including during the day's follow-up visit? Yes No

If yes, describe each interruption:

Date	Duration	If yes, reason for interruption
____/____/ _____ (DD/MM/YYYY)	____ days  Ongoing	 AE*; If yes, specify which one: _____  Radiotherapy  Surgery  Other, specify: _____
____/____/ _____ (DD/MM/YYYY)	____ days  Ongoing	 AE; If yes, specify which one: _____  Radiotherapy  Surgery  Other, specify: _____

(Dynamic table: rows can be added if more than two modifications are observed)

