3.8 Decision concerning sunitinib treatment

Participating physician's decision following this follow-up visit

Continue treatment, date of day 1 of next cycle: ____ / ____ / ____ (DD/MM/YYYY)

Dose and dosage regimen:

50 mg/day, 4 weeks followed by a 2-week break

Other, specify: _____

Termination of current treatment, date stopped: ____ / ____ / ____ (DD/MM/YYYY)

Break from therapy

Change of line of therapy (fill in the end of treatment appraisal form)

Continued break from therapy

Resumed sunitinib treatment, date resumed: ____ / ____ / ____ (DD/MM/YYYY)

In the event of treatment termination, the physician is directed to the end of treatment form.

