14.7. Appendix 7: Intervention by nurse

RENACALL STUDY

Evaluation of the impact of a therapy management platform on the management of patients suffering from advanced/metastatic renal cell carcinoma and receiving first line treatment with sunitinib, versus standard follow-up

INTERVENTION BY NURSE

A. MANAGEMENT BY THE THERAPY MANAGEMENT PLATFORM ¹

The patients will be monitored not only in the standard manner, but also via the therapy management platform.

Calls shall be made by nurses specially trained for this role, from a centralised platform based in the Paris region. If necessary, the nurses may be assisted by physicians from the therapy management platform.

The aim of these calls is to support the patients in the management of their treatment by listening to and advising them, implementing preventive measure and taking actions when deemed necessary; the purpose of these calls is to support patients in the management of their sunitinib treatment.

Call frequency is presented in the following figure:

[figure not shown]

Figure 1. Call frequency for patients

The chosen rate is of:

- For the first two cycles, C1 and C2: 5 calls during the first 5 weeks of each cycle (i.e. one call per week; no call during week 6 as the patients are usually seen in consultation),
- For cycles 3 and 4: 2 calls per cycle on weeks 2 and 4.

These calls will be made for patients treated with Sutent®; in the event of termination of treatment during the follow-up period, the call following termination will close the intervention. In the event of cycle start postponement, the first call made shall be postponed to match the expected organisation (cycles 1 and 2: first call during week 1 of the cycle; cycles 3 and 4: first call during week 2 of the cycle).

¹ Information obtained from the RENACALL protocol

B. DATA COLLECTED

	1 st call	Follow-up calls	Freephone number call
General information concerning the interview	X		
Patient's general condition	X	X	X
Introduction: treatment initiation	X		
Introduction: support follow-up and treatment resumption		X	X
Treatment compliance (+ Morisky at W4 cycles 1, 2 and 4)	X	X	X
Initial and support prescriptions	X		
Additional prescriptions		X	X
Care pathway (medical procedures, hospitalisation, emergencies)	X	X	X
Examination and additional tests follow-up	X	X	X
Tolerance, reported side effects	X	X	X
Monitoring of side effects and corrective actions		X	X
Setting appointments	X	X	X

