Name : _____	 antiemetic  antidiarrhoeal  anti-neutropenic  antihypertensive  mouthwashes and local anaesthetics  emollients, moisturising creams  analgesics  anti-gastro-oesophageal reflux agents  bisphosphonates  Other, specify _____	 Date first taken: _____ / _____ / _____ (DD/MM/YYY)  when necessary	 Ongoing  Stopped, End date _____ / _____ (DD/MM/YYY Y)	 Curative  Preventive  Not available	 Dosage regimen: _____ doses _____ time(s) per day for _____ weeks  Not available	Recommendations: _____  Not available

Instruction: identifying all treatments available to the patient will allow the nurses to adapt the advice and actions to be implemented. The nurses will have received an anonymised copy of the patient's prescriptions from the physician

- 5- **If first call:** Could you tell me when you took Sutent® for the first time? Taken Not taken

- *If taken*, Date first taken: ___/___/___ (DD/MM/YYYY)
- *If not taken*, Why haven't you started the Sutent® treatment?
 - I forgot to start
 - I am stressed / anxious at the thought of taking it
 - Other, specify: _____

↳ Do you have any questions, or topics you would like to discuss before starting to take your treatment? *[Guide and advise the patient. Notify the oncologist if major problem]*

D.2.2. Introduction of the "Regular" interview (excluding the first call of the first cycle)

Info: The introduction discussion is a 'free' discussion between the nurse and the patient, to be held during each call. It concerns the patient's overall health, in order to win his/her trust at the start of the interview. These data will not be collected, unless an AE is declared.

- How have you been since our last talk? How is it going?

- ↳ *If resuming a cycle, a tumour evaluation should have been conducted during week 6*
 - Date of last tumour evaluation: ___/___/___ (DD/MM/YYYY)
 - Response: RC / RP / SD / PD / NE, reason _____
 - ↳ *If answer: encourage the patient during the conversation*

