8.2.5.4. Response to sunitinib treatment

Analysis population: FAS population

Analysis:

The response to treatment will be assessed by the investigator based on RECIST v1.1 criteria (complete response, partial response, stable disease or progression) and will be described at each follow-up time (at the end of cycles 1, 2 and 4) (cf. section 8.2.3. Description of patients during the follow-up period).

The best response obtained during treatment with sunitinib will be identified from the responses assessed according to RECIST v1.1 criteria. “Unevaluable” responses will not be included in the definition of the best response.

The proportion of patients with a complete or partial best response during the follow-up period (objective response rate) will be estimated.

The last response assessed during the study will also be estimated.

The analysis will be performed on an overall basis and by the number of calls made by the call center.

Analysis of response will also be assessed on the FAS population imputing missing data points by failure (= progression).

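### The W24 case report form has room for one tumour evaluation but covers two cycles, so an evaluation at about W18 or W24 can go unrecorded and change best response, ORR or last response

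*Protocol*

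**What the plan says.** **Visit form.** Protocol Appendix 6, CRF 3.1, asks: "Has a tumour evaluation been carried out since the last visit dated [date of last recorded visit". If yes, there is one examination date, a choice of imaging methods and one RECIST v1.1 response. CRF section 3 sets the timing: "Identical follow-up data collection by the physician for all three visits: W6, W12 and W24". There is no visit at the end of cycle 3. Other parts of the same CRF can grow. CRF 3.5 carries the note "Dynamic table: rows can be added if more than two modifications are observed", and the tables in CRF 3.7 have similar notes. CRF 3.1 has no such note and no rule for choosing between evaluations.

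**Call script.** Protocol Appendix 7, D.2.2, tells the nurse: "If resuming a cycle, a tumour evaluation should have been conducted during week 6". The cycle-start calls are for cycles 2, 3 and 4. The information note at the head of D.2.2, describing the introductory conversation, says: "These data will not be collected, unless an AE is declared".

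**End-of-treatment form.** CRF section 4 has a field for best RECIST response to first-line sunitinib. CRF 3.8 says: "In the event of treatment termination, the physician is directed to the end of treatment form". Protocol section 8.2 (End of study), after listing completion of four cycles as one way of leaving the study, says an end-of-treatment sheet is completed when the study ends.

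**SAP.** Section 8.2.5.4 says: "The best response obtained during treatment with sunitinib will be identified from the responses assessed according to RECIST v1.1 criteria". Unevaluable responses are ignored. The ORR is the proportion with complete or partial best response, and the last response assessed is also reported. Section 7 makes observed cases the main approach and adds a response analysis that counts missing as progression.

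**The concern.** The W6 and W12 forms each cover one six-week cycle, so one slot matches one expected evaluation. The W24 form covers twelve weeks with the same single slot. If a patient was evaluated near both W18 and W24, one result has nowhere to go, and the physician chooses which to enter without guidance.

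ORR is a stated secondary objective, and best response is a maximum over evaluations, so leaving one out can hide a response. If the W18 result is entered, it also appears in the SAP's end-of-cycle-4 display (Table 24) and becomes the last response.

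Only patients who reach cycle 4 can be affected. The SAP also shows response by number of calls. Its compliance rule (SAP 5.2) needs at least 3 successful calls in each of cycles 1 and 2, so very early stoppers cannot meet it. The loss may therefore fall unevenly across that display.

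**Working it through.** **Timeline.** One cycle is 6 weeks, so cycles 1 to 4 end at W6, W12, W18 and W24.

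| Time | Evaluation expected by call script | Visit form |
|---|---|---|
| W6 | yes (before cycle 2) | yes, one slot |
| W12 | yes (before cycle 3) | yes, one slot |
| W18 | yes (before cycle 4) | none |
| W24 | not stated | yes, one slot for W12 to W24 |

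The calls end with cycle 4 ("For cycles 3 and 4: 2 calls per cycle on weeks 2 and 4"), so the script says nothing about W24. That evaluation comes from the visit form.

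**The plan's own precision figure.** Protocol 8.5 uses i = 1.96 × √(p(1−p)/n). At p = 50% and n = 100 this is 1.96 × √(0.25/100) = 9.8 points, as stated. At p = 30% it is 1.96 × √(0.21/100) = 9.0 points. The formula was chosen for the primary endpoint, and there is no sizing for ORR.

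**Direction for one patient.** Let the earlier best response, the W18 result and the W24 result each be CR, PR, SD, PD or not assessable, which gives 5 × 5 × 5 = 125 patterns. Keep the earlier result and only one of the two later ones, and apply the SAP rule. The counts are the same whichever is kept:

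| All evaluations → recorded | Patterns |
|---|---|
| responder → responder | 80 |
| responder → non-responder | 16 |
| responder → missing | 2 |
| non-responder → non-responder | 24 |
| non-responder → missing | 2 |
| missing throughout | 1 |

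No pattern turns a non-responder into a responder. These are unweighted counts, not probabilities.

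**Direction for the ORR.** Let N be the number evaluable if everything were kept, R the true responders, k the responders recorded as non-responders, and m the non-responders who become missing.

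- Observed cases: ORR = (R − k)/(N − m). This exceeds R/N when m > N × k/R.
- Missing = progression: ORR = (R − k)/N, which cannot exceed R/N.

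With N = 100 and R assumed at 20, 30 or 40 (the documents give no expected ORR):

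| k | m | Observed-case ORR, % (R = 20 / 30 / 40) | Missing = progression, % |
|---|---|---|---|
| 0 | 0 | 20.0 / 30.0 / 40.0 | 20.0 / 30.0 / 40.0 |
| 5 | 0 | 15.0 / 25.0 / 35.0 | 15.0 / 25.0 / 35.0 |
| 0 | 10 | 22.2 / 33.3 / 44.4 | 20.0 / 30.0 / 40.0 |
| 2 | 10 | 20.0 / 31.1 / 42.2 | 18.0 / 28.0 / 38.0 |

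For k = 2 the break-even m is 10.0, 6.7 and 5.0. The values of k and m are illustrations of direction only. A rise needs patients with nothing else evaluable on their forms, so a fall is the likelier outcome.

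**Last response.** It is right if W24 is entered. If W18 is entered it can be wrong either way, for example a response at W18 shown in place of progression at W24.

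**The case against.** The strongest reply is that the loss may be small or nil. CRF 3.1 only asks whether an evaluation was done, physicians follow usual practice, and no passage requires a scan at W24. If the physician enters the better result, best response is unaffected. If the end-of-treatment form is completed for everyone, as Protocol 8.2 suggests, its best-response field would cover an unrecorded scan. SAP 8.2.5.4 does not confine best response to the three visit forms; it leaves the source open. ORR is secondary and descriptive, and no tests are planned.

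Most of this stands, and it limits the point. It does not remove it, because each safeguard depends on something the documents leave unsettled: an unwritten choice by the physician, two passages that differ on who gets the end-of-treatment form, and a field the SAP does not name.

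Several stronger readings are tempting but unsupported:

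- **The script expects two evaluations between W12 and W24.** It implies only the one at about W18.
- **The bias can only be downwards.** That is true of a patient's best response and of the missing = progression ORR. The observed-case ORR can rise through a smaller denominator.
- **The call system holds the W18 result.** The script does have date and response fields, but under a note that the conversation's data are not collected. Tumour response is not in the lists of call data in Protocol 8.4.2 or SAP 2.2.
- **Only patients who stop treatment get the end-of-treatment form.** CRF 3.8 does not say only, and Protocol 8.2 reads otherwise.
- **The loss is a few points of ORR.** Assuming that 60 to 75 of 100 patients have both scans and 2 to 6% of them respond at W18 only gives 60 × 0.02 = 1.2 to 75 × 0.06 = 4.5 patients. Neither input is in the documents.

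**Conclusion.** The structural gap is real. A patient evaluated near both W18 and W24 can have only one result on the visit forms, with no rule for which. Such a patient's best response, and the missing = progression ORR, can only fall or stay the same. The observed-case ORR is more likely to fall but can rise. The last response is wrong whenever a W18 result that differs from the W24 result is entered in its place.

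The size cannot be derived from the documents. It depends on how many patients have both evaluations, which one is entered, and whether the end-of-treatment field is completed and used. The primary endpoint and the sample size are not touched. The change is still worth making, because it protects a stated secondary objective at little cost.

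**What to change.** - **CRF 3.1:** make it a repeatable table with date, method and response for each evaluation since the last visit, in the manner of CRF 3.5 and 3.7.
- **Completed forms:** ask physicians about any unrecorded evaluation between W12 and W24 in every patient who reached cycle 4. Do not rely on call-system data to trigger the query, since those data may not exist. Protocol section 5 schedules the end of data collection for November 2018, so this step may matter more than the form change.
- **SAP 8.2.5.4:** take best response over all recorded evaluations up to the end of cycle 4, take last response from the latest evaluation date, state the ORR denominator, and say whether the end-of-treatment best-response field counts as a source.
- **Protocol 8.2 (End of study) and CRF 3.8:** reconcile them on which patients have the end-of-treatment form completed.

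The cost is one table, a few sentences, some queries and a little extra data entry. No scans are added; only results that already exist are entered.
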